#### Schematic of study design

For elaborated details on study design please refer to the study design section of the protocol .

# 1.2 Study objectives, endpoints and estimands

| Objective(s)  | Endpoint(s)   |  |
|---|---|--|
| Primary objective(s)  | Endpoint(s) for primary objective(s)  |  |
| • The primary objective of this study is
to demonstrate superiority of inclisiran
+/- behavioural support compared to
standard of care + behavioural support
in a primary care setting, in terms of the
percentage change in LDL-C from
baseline to Day 270 in adults with
elevated LDL-C. | 
 
Percentage change in LDL-C from baseline to Day 270.
 
  |  |
| Secondary objective(s)  | Endpoint(s) for secondary objective(s)  |  |
| The secondary objectives of this study are to
evaluate the implementation of inclisiran +/-
behavioural support compared to standard of
care + behavioural support in a primary care
setting using the following assessments:   |   |  |
| • Measures of patient satisfaction using the validated CSQ-8 (Client Satisfaction Questionnaire) administered after treatment at day 90.  | • Mean difference in total score using the validated CSQ-8 (Client Satisfaction Questionnaire) administered after treatment at day 90.  |  |
| • Measures of patient activation and
empowerment using the validated Patient
Activation Measure (PAM) questionnaire
administered after treatment at day 90.  | • Mean difference in total score using the validated Patient Activation Measure (PAM) questionnaire administered after treatment at day 90.   |  |
| • Measures of adherence to cardiovascular
disease self-management using the
validated Patient Activation Measure
(PAM) questionnaire administered after
treatment at day 90 and using assessment
of medication adherence during the study
period.   | • The frequency and percentages of subjects in the four levels of the PAM scores (below) will be summarized. Highly activated patients (level 3 and level 4) are more likely to adhere to cardiovascular self-management and thus medication adherence. |  |
|   | Level 1: Disengaged and overwhelmed   |  |
|   | Level 2: Become aware but still struggling  |  |
|   | Level 3: Taking action  |  |

| Γ  |   |
|--|---|
|  | Level 4: Maintaining behaviors and pushinng further.  |
| • A process evaluation conducted using the
Consolidated Framework for
Implementation Research (CFIR) which
will explore inclisiran delivery at three
levels:                                     | This SAP does not intend to describe
methodology adopted for the Process
Evaluation Sub-study data analysis. This
study objective is listed for completeness
only. For further detail on the process  |
| 1. Level 1: Feasibility and acceptability of delivery models for inclisiran to patients  | evaluation and planned analyses, please
refer to section 4.3 of the Protocol. The
analysis results will be reported in final  |
| 2. Level 2: Feasibility and acceptability of delivery models for inclisiran to providers (inner setting)   | CSR.  |
| 3. Level 3: Wider 'transactability' of the proposed delivery models (outer setting)  |   |
| 4. The service costs of each delivery model  |   |
| 5. The acceptability and perceived sustainability of patient identification and referral routes  |   |
| Data from the process evaluation will initially
analysed blind to trial outcomes (this analysis
will then be used to compare and explain any
differences in outcomes between intervention
arms). |   |
| • Serious adverse event profile  | 
 
Incidence, severity and relationship to
the study drug of treatment emergent
adverse events, serious adverse events
and adverse events leading to treatment
discontinuation.
 
Incidence of on-treatment and post-
 
 |
|  | treatment deaths.   |
|  |   |
|  |   |
|  |   |

# 2 Statistical methods

## 2.1 Data analysis general information

All analyses will be performed by Novartis or a designated CRO. The most recent version of SAS available in the statistical programming environment of Novartis or the designated CRO will be used for the analysis.

Final analysis will be conducted after all participants either complete the study or discontinued early. Final analyses will be reported in Final CSR.

Additional analysis may be conducted to evaluate the impact of COVID-19 pandemic, if required.

## 2.1.1 General definitions

#### Study day:

Study day will be defined as the number of days since the date of first dose of study treatment. The date of first dose of study treatment will be defined as Day 1 and the day before the first dose of study treatment will be defined as Day -1.

Therefore, for a particular date, study day will be calculated as follows:

| Novartis | Confidential | Page 12 of 37           |
|----------|--------------|-------------------------|
| SAP      |              | Study No. CKJX839A1GB01 |

For dates on or after the first date of study treatment,

Study day = Assessment date – Date of first dose of study treatment + 1;

For dates prior to the first date of study treatment,

Study day = Assessment date – Date of first dose of study treatment.

In case, participant has been randomized but has not received study treatment then randomization visit day will be considered as Day 1.

#### **Baseline definition:**

The baseline assessment is defined as the last non-missing assessment (scheduled or unscheduled) collected before the first dose of study treatment (Day 1) or randomization visit day, if no study treatment has been received.

#### **Post-baseline measurement:**

Post-baseline values are defined as those measurements that were collected after the first dose of study treatment or randomization visit if no study treatment has been received.

When change from baseline is of interest the following formula will be used for each scheduled visit and time-point where baseline and post-baseline values are both available:

Change from baseline = post-baseline value – baseline value.

Percent change from baseline = (change from baseline / baseline value)\*100.

#### Visit windows:

If there is more than one observation in a specific window, then the one closest to the target day will be used for analysis. If there are two or more observations that are equally distant to the target day and within the analysis window, the first of these observations will be selected for analysis. Observations that are out of the analysis window below will be classified as unscheduled visits and will not be included in the primary and key secondary efficacy analysis. However, all data will be included in the subject data listings.

As shown in the table below, all visit will apply a window of  $\pm$  14 days.

 Table 2-1
 Analysis windows for each scheduled visit

| Visit Name         | Target day | Analysis window |
|--------------------|------------|-----------------|
| Screening/Baseline | -1         | Day -14 to -1   |
| Visit 1            | 1          | Day 1 to 14     |
| Visit 2            | 90         | Day 76 to 104   |
| End of Study       | 270        | Day 256 to 284  |

\*Day 1 is defined as day of initiation of study drug administration or randomization visit day if no study treatment has been received.

#### 2.2 Analysis sets

Screened Set (SCR) will include all participants who provided study informed consent.

**Randomized set (RAN)** will consist of all participants who received a randomization number, regardless of whether study treatment received or not.

| Novartis | Confidential | Page 13 of 37           |
|----------|--------------|-------------------------|
| SAP      |              | Study No. CKJX839A1GB01 |

**Full Analysis Set (FAS)** will consist of all randomised participants with the exception of those mis-randomised participants who did not receive study drug. Mis-randomised participants are defined as not qualified for randomisation and are inadvertently randomised into the study. According to the intent to treat principle, participants will be analysed according to the treatment they have been assigned to during the randomisation procedure. The FAS will be used in analyses for the primary, secondary, **and the study** efficacy objectives.

**Safety Set (SAF)** will consist of all participants who received at least one dose of study treatment. Participants will be analysed according to the study treatment received. This will be the primary population for the safety analyses.

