Enrollment	Point/time of participant entry into the study at which informed consent must be obtained	
Estimand	A precise description of the treatment effect reflecting the clinical question posed by the trial objective. It summarises at a population-level what the outcomes would be in the same patients under different treatment conditions being compared. Attributes of an estimand include the population, variable (or endpoint) and treatment of interest, as well as the specification of how the remaining intercurrent events are addressed and a population-level summary for the variable.	
Healthy volunteer	A person with no known significant health problems who volunteers to be a study participant	
Intercurrent events	Events occurring after treatment initiation that affect either the interpretation or the existence of the measurements associated with the clinical question of interest (e.g. treatment discontinuation, use of prohibited medications, deviation in background treatment or death).	
Investigational drug/ treatment	The drug whose properties are being tested in the study - KJX839/Inclisiran for Injection (sub-cutaneous use), is a sterile formulation of inclisiran sodium in water for injection packaged in vial or glass pre-filled syringe (PFS) presentations; also referred to as study drug	
Medication number	A unique identifier on the label of medication kits	
Mis-randomised participants	Mis-randomised participants are those who were not qualified for randomisation and who did not take study treatment, but have been inadvertently randomised into the study	
Other treatment	Treatment that may be needed/allowed during the conduct of the study (i.e. concomitant or rescue therapy)	
Part	A sub-division of a study used to evaluate specific objectives or contain different populations. For example, one study could contain a single dose part and a multiple dose part, or a part in participants with established disease and in those with newly-diagnosed disease	
Participant	A trial participant (can be a healthy volunteer or a patient)	

Participant number	A unique number assigned to each participant upon signing the informed consent. This number is the definitive, unique identifier for the participant and should be used to identify the participant throughout the study for all data collected, sample labels, etc.

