Period	The subdivisions of the trial design (e.g. Screening, Treatment, Follow-up) which are described in the Protocol. Periods define the study phases and will be used in clinical trial database setup and eventually in analysis
Personal data	Participant information collected by the Investigator that is coded and transferred to Novartis for the purpose of the clinical trial. This data includes participant identifier information, study information and biological samples.
Premature participant withdrawal	Point/time when the participant exits from the study prior to the planned completion of all study drug administration and/or assessments; at this time all study drug administration is discontinued and no further assessments are planned
Randomisation number	A unique identifier assigned to each randomised participant
Screen Failure	A participant who did not meet one or more criteria that were required for participation in the study
Source Data/Document	Source data refers to the initial record, document, or primary location from where data comes. The data source can be a database, a dataset, a spreadsheet or even hard-coded data, such as paper or eSource
Start of the clinical trial	The start of the clinical trial is defined as the signature of the informed consent by the first participant
Study treatment	The study treatment, KJX839/Inclisiran for Injection (sub-cutaneous use), is a sterile formulation of inclisiran sodium in water for injection packaged in vial or glass pre-filled syringe (PFS) presentations
Study treatment discontinuation	When the participant permanently stops taking any of the study drug(s) prior to the defined study treatment completion date (if any) for any reason; may or may not also be the point/time of study discontinuation
Treatment arm/group	A treatment arm/group defines the dose and regimen or the combination, and may consist of 1 or more cohorts.
Treatment of interest	The treatment of interest and, as appropriate, the alternative treatment to which comparison will be made. These might be individual interventions, combinations of interventions administered concurrently, e.g. as add-on to standard of care, or might consist of an overall regimen involving a complex sequence of interventions. This is the treatment of interest used in describing the related clinical question of interest, which might or might not be the same as the study treatment.

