8.2 Screening

Screening (Days -14 to -1)

Eligibility and recruitment to the study will be optimised by using NWEH's proven feasibility and recruitment system FARSITE.

FARSITE, is a tool for searching, finding, and contacting patients with research opportunities, whilst still preserving their confidentiality. The principle behind FARSITE is to maintain patient confidentiality by anonymising the information given to researchers, and only allowing GPs to decide whether their patient should be contacted. Researchers do not have access to individual patient records, information about individuals who meet the criteria for a protocol is only available to the patient's GP practice. All identifiable records are seen only by the GP as the data controller, and a handful of NWEH and Salford Royal Foundation Trust (SRFT) technical staff by exception to maintain the FARSITE system. Researchers see only deidentified records, as the datasets are held in two different databases stored securely on the N3 NHS network (see Figure 8-1).

Figure 8-1 FARSITE System Overview

NWEH researchers will use the FARSITE Feasibility view which contains anonymised data during the initial stages of recruitment to see how many patients match the study protocol; the numbers of patients matching each inclusion criterion; and the numbers belonging to each registered GP practice. FARSITE will identify and be used to contact the most suitable GP practices within Greater Manchester to ascertain the maximum number of patients from up to 30 GP practices. Once the list of potential patients is identified, the GP will review the patient's medical records manually and confirm eligibility. There are no screening laboratory tests

required to be performed for this study, total cholesterol inclusion criteria will be determined by the pathology results available in the patients EMR.

The following procedures will be performed within 14 days prior to study treatment:

- Informed consent
- Assessment of inclusion and exclusion criteria
- Demographics
- Vital signs (height,
- CV risk (smoking status, diet, exercise, HbA1c if available)
- Lipid profile
- Randomisation

It is permissible to re-screen a participant if s/he fails the initial screening; however, each case must be discussed and agreed with the Sponsor on a case-by-case basis and can be only once per patient during the study period.

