12.1 Analysis sets

The Full Analysis Set (FAS) comprises of all randomised participants with the exception of those mis-randomised participants who did not receive study drug. Mis-randomised participants are defined as not qualified for randomisation and are inadvertently randomised into the study. According to the intent to treat principle, participants will be analysed according to the treatment they have been assigned to during the randomisation procedure. The FAS will be used in analyses for the primary, secondary, **and the efficacy** objectives.

The Safety Set includes all participants who received at least one dose of study treatment. Participants will be analysed according to the study treatment received. This will be the primary population for the safety analyses.

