#### 5.6 Rule of exclusion criteria of analysis sets

The protocol deviations (PD) and other criteria leading to complete exclusion from analyses sets are provided in below table, which may be updated prospectively and will be finalized before study DBL.

| Protocol Deviation |  | Excluding from
Analysis set |     |     |
|--------------------|--|--------------------------------|-----|-----|
| ID                 | Desctiption  | RAN                            | FAS | SAF |
| INCL01A            | No study informed consent prior to performing study assessments  | Х                              | Х   | Х   |
| INCL01B            | No signed informed consent exists at site  | Х                              | Х   | Х   |
| INCL02             | Participant's age < 18 years at screening visit  |                                |     |     |
| INCL03A            | Participant not on statin therapy and intolerance not documented   |                                |     |     |
| INCL03B            | Participant is indicated to have partial statin intolerance but
not documented  |                                |     |     |
| INCL04             | Participant's total cholesterol not available at screening visit
or is <4mmol/L (160mg/dL)  |                                |     |     |
| INCL05             | Participant's lipid-lowering therapy at study entry not stable
for ≥ 30 days before screening visit   |                                |     |     |
| EXCL01             | Participant has medical or surgical history that might limit the
EXCL01 individual's ability to take study treatments for the duration of
the study and/or put the participant at significant risk |                                |     |     |
| EXCL02             | Current or planned renal dialysis or transplantation   |                                |     |     |

 Table 5-4
 Protocol deviation criteria leading to exclusion from analysis sets

| Protocol Deviation |  | Excluding from
Analysis set |     |     |
|--------------------|--|--------------------------------|-----|-----|
| ID                 | Desctiption  | RAN                            | FAS | SAF |
| EXCL03             | Participant had acute coronary syndrome or stroke less than 4 weeks before the screening visit   |                                |     |     |

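### As worded, the Full Analysis Set removes mis-randomised controls whenever they are found but mis-randomised inclisiran participants only if undosed, and this conflicts with SAP Table 5-4

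*SAP*

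**What the plan says.** The FAS serves the primary and secondary efficacy analyses. SAP 2.2 makes it "all randomised participants with the exception of those mis-randomised participants who did not receive study drug", and protocol 12.1 gives the same rule. Both sections then explain the term: "Mis-randomised participants are defined as not qualified for randomisation and are inadvertently randomised into the study". The protocol glossary words it differently and builds dosing into the definition: "not qualified for randomisation and who did not take study treatment, but have been inadvertently randomised into the study".

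The glossary also fixes what the drug is. The investigational drug is inclisiran, "also referred to as study drug", and the entry for study treatment reads "The study treatment, KJX839/Inclisiran for Injection (sub-cutaneous use), is a sterile formulation of inclisiran sodium". Protocol 6.5.2 gives injections on Day 1 and Day 90 to Groups 2 and 3 only. Group 1, which SAP 1.1 calls the control group, has its usual lipid-lowering medication and behavioural support.

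SAP 5.6 (Table 5-4) lists the deviations that remove a participant from each analysis set. For the FAS it marks the two consent deviations (INCL01A, INCL01B), site closure for GCP reasons (OTH03), and dosing of someone who was never randomised (TRT02). All other inclusion and exclusion deviations are unmarked, and there is no row for mis-randomisation.

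**The concern.** The exclusion condition has two parts: randomised although ineligible, and not given study drug. In a placebo-controlled trial the second part can be met or failed in every arm. Here it is automatically true for a control treated as assigned, and false for an inclisiran participant from the first injection onwards.

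Timing adds to the imbalance. Randomisation takes place at the screening/baseline visit, up to 14 days before treatment (protocol 8.2). In Groups 2 and 3 only an error found before the first injection, or a participant who is never dosed, leads to exclusion. In Group 1 an error found at any time does. Protocol 11.3 requires full verification of the eligibility criteria at monitoring, so late findings are foreseeable.

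What is at stake is the comparability of the arms in the primary LDL-C comparison and in PAM and CSQ-8, the two outcomes that drive the sample size. A second risk is practical: one programmer following SAP 2.2 and another following Table 5-4 would build different analysis sets, and the choice would be made on open-label data.

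**Working it through.** **1. The rule applied to each case (SAP 2.2 text)**

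| Mis-randomised participant | Received inclisiran? | In the FAS? |
|---|---|---|
| Group 1, treated as assigned | No | No |
| Group 2 or 3, not dosed | No | No |
| Group 2 or 3, dosed | Yes | Yes |

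Under Table 5-4 read alone, all three stay in, provided that consent was valid and the site was not closed for GCP reasons. The glossary definition of mis-randomised gives the same three answers as SAP 2.2.

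A looser reading, in which study drug covers the control regimen, does not fit the SAP. In SAP 2.1.1 the study-day, baseline and visit-window rules each add a fallback to the randomisation visit for participants who had no study treatment. The FAS sentence has no such fallback.

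**2. The plan's sample size**

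Inputs (protocol 12.8, SAP 3): effect size 0.3, 90% power, one-sided 0.025, 20% drop-out.

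- n per arm = 2(1.960 + 1.282)² / 0.3² = 234
- 234 / 0.8 = 293, against the stated 300
- With 240 evaluable per arm (300 × 0.8), power is 90.8%

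For LDL-C (SD 30 in control, 20 with inclisiran, difference 10): SE = √(900/240 + 400/240) = 2.33. Power is 99.0% at one-sided 0.025 and 98.0% at 0.0125, the first Holm step.

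**3. Size of the imbalance**

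The documents give no mis-randomisation rate, so these are assumptions:

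- m = mis-randomised share, equal in each arm, 0.5% to 5%
- u = share of mis-randomised inclisiran participants never dosed, 0% to 50%
- D = difference in percentage LDL-C change between mis-randomised and other participants, the same in each arm

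Formulas:

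- controls dropped = 300m
- dropped per inclisiran arm = 300mu
- share of the inclisiran FAS that is mis-randomised: r = m(1 − u)/(1 − mu)
- with everyone kept, mD is added to both arm means and cancels; under the rule, rD is added to the inclisiran mean only, so the shift in the treatment difference is rD

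| m | u | Controls dropped | Dropped per inclisiran arm | r | Shift, D = 10 | D = 20 | D = 40 |
|---|---|---|---|---|---|---|---|
| 0.5% | 0% | 1.5 | 0 | 0.0050 | 0.05 | 0.10 | 0.20 |
| 0.5% | 50% | 1.5 | 0.75 | 0.0025 | 0.03 | 0.05 | 0.10 |
| 1% | 0% | 3 | 0 | 0.0100 | 0.10 | 0.20 | 0.40 |
| 1% | 50% | 3 | 1.5 | 0.0050 | 0.05 | 0.10 | 0.20 |
| 2% | 0% | 6 | 0 | 0.0200 | 0.20 | 0.40 | 0.80 |
| 2% | 50% | 6 | 3 | 0.0101 | 0.10 | 0.20 | 0.40 |
| 5% | 0% | 15 | 0 | 0.0500 | 0.50 | 1.00 | 2.00 |
| 5% | 50% | 15 | 7.5 | 0.0256 | 0.26 | 0.51 | 1.03 |

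The same formula applies to PAM and CSQ-8. At m = 5% and u = 0, each full standard deviation by which mis-randomised participants differ moves the comparison by 0.05 SD, against the planned 0.3 SD.

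**4. Power under the rule**

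With 0.8 × 300(1 − m) controls and 0.8 × 300(1 − mu) per inclisiran arm, power for effect size 0.3 stays between 89.7% and 90.7%, and LDL-C power at one-sided 0.025 between 98.8% and 99.0%. Power is not the problem.

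**The case against.** **Table 5-4 may govern.** If it does, ineligible controls stay in and the asymmetry disappears. SAP 2.3.1 points the same way, because it tabulates unmet selection criteria on the FAS. This stands as a limit on certainty: the documents do not settle which rule prevails. It does not remove the defect, since the FAS definition itself says something else.

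**Mis-randomised is a narrow group.** The term requires inadvertent randomisation as well as ineligibility. A GP reviews the records, and all criteria are confirmed before randomisation. Protocol 8.2.1 treats participants randomised in error as an example of those who fail to start treatment. This supports a low rate, though no figure is given.

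**Some inclisiran participants leave too.** An error found between randomisation and the first injection can remove a Group 2 or 3 participant. This is correct, and u covers it.

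**Keeping the controls may add little.** Some may have no Day 270 value and would then enter the primary analysis by imputation. PAM and CSQ-8 use observed data only. This is fair, but it is no reason for a rule that differs by arm.

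**A stronger reading on frequency fails.** A reader might infer that ineligibility could be common, because "total cholesterol inclusion criteria will be determined by the pathology results available in the patients EMR" (protocol 8.2) while deviation INCL04 refers to "total cholesterol not available at screening visit". The documents do not support this. Protocol 8.2 gives no age for the record value. INCL04 can equally mean that no record result was to hand at that visit. Someone who qualified on the prescribed source was qualified. INCL04 is also unmarked for the FAS.

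**Conclusion.** The point holds as a defect of definition. Under the FAS text, a mis-randomised control treated as assigned is excluded whenever the error is found, and a mis-randomised inclisiran participant only if undosed. Table 5-4 contradicts that text.

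The size rests on assumed rates. At 0.5% to 5% mis-randomised per arm and D = 10, the LDL-C difference shifts by at most 0.05 to 0.5 points, against a planning difference of 10. Even D = 40 at the 5% rate gives 2.0 points. The documents do not indicate the direction of any shift.

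Two further inferences go too far. One is that ineligible controls will certainly be lost, which the conflict with Table 5-4 leaves open. The other is that the plan abandons intention to treat: the sentence invoking that principle concerns analysis by assigned arm, which the plan respects. The narrower criticism is that a set described in those terms should not select participants by arm and dosing. The change should be made, but the primary conclusion is unlikely to turn on it.

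**What to change.** In SAP 2.2 and protocol 12.1, define the FAS as all randomised participants in all three arms, apart from the consent and GCP-closure exclusions already in Table 5-4, and delete the study-drug condition. TRT02 concerns people who were never randomised, so they fall outside the set in any case.

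If mis-randomised participants must be removed, do it on facts fixed before randomisation, judged identically in every arm and regardless of dosing, and add a matching row to Table 5-4. Under either option, bring the glossary definition into line.

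The cost is one sentence in each document, a glossary edit and, for the second option, a table row. No new data are needed and the planned numbers and power are unchanged. SAP 5.6 already allows the table to be revised until database lock.
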